5.2 RECRUITMENT

Potential study participants will be recruited through standard means or by referral. Any materials used for study advertising generated by the investigational site will be approved by the local IRB to use.

5.3 SCREENING

Subject eligibility assessment is to be performed based on data available to the investigator at the time of screening. This initial screening phase may include review of existing subject information (previously performed angiography, radiographs, laboratory studies, medical history, physical examination, etc.). Subjects who appear to meet the enrollment criteria should be asked to participate in this study. Subjects asked to participate should be recorded on the study screening log.

5.4 INFORMED CONSENT

Informed consent is a process that is initiated prior to the subject's agreeing to participate in the study and continues throughout the subject's study participation. The process must be documented. A verbal explanation will be provided to the subject (or legally authorized representative) as to the purpose and requirements of this study. Details of the study should include (but are not limited to): the study objectives, alternative treatments, the need to return follow-up visits, participation is voluntary, and there is no penalty for withdrawal, the potential risks/benefits for participation and contact information to ask questions or voice concerns. The participants should have the opportunity to discuss the study with their surrogates or think about it prior to agreeing to participate.

Consent to participate in this study must be obtained in written format in a language understood by the potential subject and using a form approved by the IRB. Each subject shall be given ample time to read the informed consent form (ICF) and ask questions to make an informed decision. All subjects must sign the informed consent form prior to any procedures/tests that go beyond the standard care for assessments for subjects with dAVF and before any study-related assessments are administered and subject-related health information can be entered in the study database.

A copy of the informed consent document will be given to the participants for their records. The rights and welfare of the participants will be protected by emphasizing to them that the quality of their medical care will not be adversely affected if they decline to participate in this study. The participants may withdraw consent at any time throughout the course of the study. For this study, written informed consent does not expire.

5.5 BASELINE EXAMINATION

Following written informed consent, the study investigator or designee will assess potential study candidates against eligibility criteria. The investigator or designee will record reason for failure in any subject actively considered for study participation.

- Review medical history to determine eligibility based on inclusion/exclusion criteria.
- Review medications history to determine eligibility based on inclusion/exclusion criteria.
- Perform medical examinations needed to determine eligibility based on inclusion/exclusion criteria.
- Schedule study visits for participants who are eligible and available for the duration of the study.
- Provide participants with specific instructions needed to prepare for the procedure.

All baseline examinations will be consistent with standard of care. Subjects who are believed by the investigator to potentially qualify will undergo the following baseline assessments:

- Demographic data
- Medical history, including smoking history
- dAVF information (Borden classification)
- Physical exam to assess dAVF symptoms
- Neurologic assessment by Modified Rankin Scale (mRS) and NIH Stroke Scale
- Hemorrhage assessment by Hunt and Hess Stroke Scale score, if applicable

Angiography

The investigator will document screening and baseline findings in the eCRF. If the subject is found to be ineligible for study participation during the baseline examination, the subject will be notified and exited from the study.

5.5.1 FEMALE SUBJECTS OF CHILDBEARING POTENTIAL

This study involves radiation during dAVF treatment as well as at follow-up visits. The investigator should follow standard medical practices to ensure that a woman of child-bearing age is not pregnant at the time of the study procedure. If a woman is pregnant at a follow-up visit that requires catheter angiogram, alternative methods to visualize the dAVF (e.g., MRA) should be used.

5.5.2 LATE SCREENING FAILURES

Study eligibility requires confirmation of anatomical characteristics that, in many cases, can only be confirmed at the time of the study procedure by angiogram. Subjects who initially appear to qualify for the study will be excluded at the time of the study procedure if the anatomical characteristics do not meet eligibility criteria or if access to the index lesion with a microcatheter is not possible or would introduce unnecessary additional risk.

5.5.3 Pre-Procedure Assessment

Routine clinical chemistry and hematology labs will need to be collected from the subject, this may be obtained between baseline and pre-procedure. Within 7 days preceding the index procedure, the subject must complete self-reported QOL questionnaire using EQ-5D.

5.6 PHIL PROCEDURE

Unless medically justified, the initial embolization procedure should be performed within 45 days of completion of the baseline assessment. The study procedure consists of pre-placement imaging, study device placement and post-placement imaging. Subjects require no special preparation for the procedure beyond standard of care for endovascular neuro-interventions. Investigators at their discretion may elect to pre-medicate with antiplatelet agents.

It is expected that the majority of PHIL initial and supplemental embolization procedures are completed under general anesthesia but a minority of procedures may be completed under conscious sedation, depending upon the center's standard of care. Heparin is administered according to standard practices. The PHIL device should be used per the IFU provided in the PHIL packaging. The PHIL procedure will be performed only by the physician investigator(s) trained by the Sponsor or its designee to perform the procedure.

The point of enrollment occurs when the PHIL liquid embolic syringe and adaptor assembly is connected to the microcatheter hub.

The investigator will record key characteristics of the device and procedure in the study's eCRF. The investigator will also record technical events/device malfunctions. Radiation exposure will be recorded as absorbed radiation dose and cumulative fluoroscopy time will be recorded. The investigator will retain and provide to the sponsor all images taken during or immediately after the study procedure (including any not specified above).

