1.2.4 SYMPTOMS/CLINICAL PRESENTATION

DAVFs can be asymptomatic or present with symptoms that range from Pulsatile Tinnitus (low risk/benign) to Intracranial Hemorrhage and Severe Neurologic Deficits (aggressive/high risk) (Table 2). Their clinical and angiographic presentation dictate the urgency of the treatment.

TABLE 2: CLINICAL PRESENTATIONS OF DAVFS

Clinical group	Manifestation
Low risk (benign)	Pulsatile tinnitus
	Orbital symptoms
Aggressive / high risk	Intracranial Hemorrhage (ICH)
	Seizures
	Altered mental status, dementia
	Hydrocephalus
	Cranial Nerve Palsies
	Loss of motor functions

Benign dAVFs tend to be found in the transverse sigmoid sinus and cavernous sinus. Patients with transverse sigmoid sinus fistulas develop pulsatile tinnitus. Patients with cavernous sinus fistulas often develop orbital symptoms, including chemosis, proptosis and conjunctival infection. ¹⁰ Aggressive/high-risk dAVFs may present with hemorrhage, non-hemorrhagic neurological deficits or even death. Patients with superior sagittal sinus fistulas develop symptoms of global venous congestions as seizures, hydrocephalus and dementia. Patients with brainstem dAVFs can develop symptoms of cranial nerve palsies and loss of motor functions. ¹⁰

The more aggressive neurological symptoms occur in cases of dAVFs with retrograde cortical venous drainage (Type II to III). Van Dijk et al. reported that the persistence of cortical venous drainage yields an annual mortality rate of 10.4%. Excluding events at presentation, the annual risk for hemorrhagic or non-hemorrhagic neurological deficits during follow-up was 8.1% and 6.9%, respectively, resulting in an annual event rate of 15%. ¹¹ Duffau et al. reported a 35% rebleeding rate in the two weeks following an initial hemorrhage. ⁶ Davies et al. reported a 20% annual mortality and morbidity rate. ¹²

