3.2 SECONDARY MEASURED OUTCOMES

The following outcomes will be measured:

- The proportion of subjects with neurological death or ipsilateral stroke within the first 30 days following completion of all PHIL treatments
- Angiographic occlusion of the pre-specified target vessel intended for treatment at procedure following completion of all PHIL treatments
- New-onset or worsening of permanent morbidity at 6 month follow-up
- New-onset intracranial hemorrhage at 6 month follow-up
- New-onset of cranial nerve palsy at 6 month follow-up
- Clinically significant technical events during the PHIL embolization procedure(s) including but not limited to reflux of embolic material, migration of the embolic material, catheter entrapment or damage, and vessel dissection.
- Device-related adverse events at procedure and 30 days
- Device-related mortality at procedure and 30 days
- Procedure related adverse events including complications of arterial puncture, contrast-induced nephropathy, radiation-induced injuries, renal and anesthesia-related complications.

New-onset of device- or procedure-related neurological deficit or adverse event, or worsening of a previous neurological complaint, disorder, deficit, or adverse event that is unresolved at 6 month follow-up even if not associated with a change in mRS.Permanent morbidity is defined as a worsening of mRS score at 6 month follow-up compared to the baseline mRS score of:

- ≥1 point in subjects experiencing a stroke
- ≥2 points in subjects experiencing neurological adverse events.

Note, worsening mRS scores associated with non-neurological causes, resulting in limitations to the subject's ability to walk or require assistance to attend to own bodily needs, will not be considered permanent morbidity. This includes medical events such as, bone fractures, muscle, ligament and tendon injuries, and other physical injuries.

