5.8 Supplemental PHIL procedure

Complete treatment of the target dAVF may require one or more PHIL procedures. Additional procedure(s) are to be scheduled and performed at the treating physician's discretion. It is estimated that up to seven (7) PHIL procedures may be required to treat the fistula. The physician shall determine the number of treatment procedures based on factors specific to each patient, such as dAVF size, number of feeders, fistulous connections, and location relative to eloquent territory. The treating physician should discontinue PHIL treatment if reflux into an eloquent artery is observed during the procedure.

The supplemental PHIL procedure consists of pre-procedure physical exam to assess dAVF symptoms, collection of routine clinical chemistry and hematology labs pre-procedure, pre-placement imaging, study device placement and post-placement imaging. Subjects require no special preparation for the procedure beyond standard of care for endovascular neuro-interventions. Investigators at their discretion may elect to pre-medicate with antiplatelet agents.

It is expected that the majority of PHIL initial and supplemental embolization procedures are completed under general anesthesia but a minority of procedures may be completed under conscious sedation, depending upon the center's standard of care. Heparin is administered according to standard practices. The PHIL device should be used per the IFU provided in the PHIL packaging. The supplemental PHIL procedure will be performed only by the physician investigator(s) trained by the Sponsor or its designee to perform the procedure.

The investigator will record key characteristics of the device and procedure in the study's eCRF. The investigator will also record technical events/device malfunctions. Radiation exposure will be recorded as absorbed radiation dose and cumulative fluoroscopy time will be recorded. The investigator will retain and provide to the sponsor all images taken during or immediately after the study procedure (including any not specified above).

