## 8. Statistical Analysis Methodology

### 8.1 General Statistical Approach

Descriptive statistics (mean, standard deviation, frequency charts, etc.) for baseline participant characteristics, subject disposition and other relevant study parameters will be reported. Where applicable, a comparison to rates reported in the scientific literature will be performed.

Tabulations of summary statistics, graphical presentations, and statistical analyses will be performed using SAS. The statistical analyses will be based on data pooled across sites in aggregate. All subset summary tables and data listings will be sorted by site and subject. The pre-procedure observations will be used as the baseline value for calculating post-procedural changes from baseline.

Continuous demographic parameters, such as the age of the subject at the time of enrollment, will be summarized using descriptive statistics (N, mean, median, standard deviation, minimum and maximum value). Categorical demographic parameters, such as gender, will be summarized as a proportion of the population.

Data obtained during the neurological examination using the Modified Rankin and self-reported EQ-5D will be summarized at each time point using descriptive statistics.

Routine clinical chemistry and hematology will be assessed by the investigator as normal/abnormal and not clinically significant/clinically significant. The incidence of abnormal and clinically significant values will be summarized and reported in frequency tables for each visit at which the data are collected.

Subject counts will be tabulated for all adverse events for the population. Adverse events will also be tabulated for events that occurred from the start of the procedure to 6 month follow-up after last embolization. Tabulated subject counts will be presented as a proportion of the population.

All recorded data will be presented in the individual data listings.

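### The mRS, NIHSS and symptom exam that serve as baseline can be 45 days or more old at the index procedure, which can misclassify permanent morbidity in either direction

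*Protocol*

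**What the plan says.** **Timing.** Protocol 5.6 sets the interval: "Unless medically justified, the initial embolization procedure should be performed within 45 days of completion of the baseline assessment". It gives no outer limit for a medically justified delay.

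**What is measured, and when.** Protocol 5.5 lists, among the baseline assessments, "Neurologic assessment by Modified Rankin Scale (mRS) and NIH Stroke Scale", together with a physical exam for dAVF symptoms. The visit schedule in the synopsis shows none of these in the PHIL procedure column. Protocol 5.5.3 adds laboratory tests and one timed questionnaire: "Within 7 days preceding the index procedure, the subject must complete self-reported QOL questionnaire using EQ-5D". The index procedure itself contains no neurological assessment: "The study procedure consists of pre-placement imaging, study device placement and post-placement imaging". Later procedures are treated differently: "The supplemental PHIL procedure consists of pre-procedure physical exam to assess dAVF symptoms" (Protocol 5.8).

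**How the baseline is used.** Protocol 3.2 and SAP 4.2 define the main outcome concerned: "Permanent morbidity is defined as a worsening of mRS score at 6 month follow-up compared to the baseline mRS score of" at least 1 point in subjects with a stroke, or at least 2 points in subjects with neurological adverse events. SAP 8.1 and Protocol 8.2 add: "The pre-procedure observations will be used as the baseline value for calculating post-procedural changes from baseline". Neither says which observation applies if there is more than one.

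**Where events in between belong.** Protocol 7.1 treats conditions present at screening as medical history and collects adverse events from enrollment, which is the connection of the PHIL syringe to the microcatheter hub. Unscheduled visits (Protocol 5.10) begin only after the study procedure.

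**The concern.** The protocol describes a disease in which neurological status can change within weeks. For patients with persistent cortical venous drainage, Protocol 1.2.4 gives annual risks of 8.1% for hemorrhage and 6.9% for non-hemorrhagic deficit. It also cites a study that "reported a 35% rebleeding rate in the two weeks following an initial hemorrhage". Protocol 1.2 says that up to 65% of patients present with intracranial hemorrhage, and recent hemorrhage is not itself an exclusion.

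In a single-arm study, within-subject change is the main internal control for natural history. If its reference value predates a bleed or a recovery, the change score mixes what happened before treatment with what happened after it. The outcomes exposed are secondary and additional. Permanent morbidity is exposed most. Less exposed are worsening of a previous deficit unresolved at 6 months, new-onset cranial nerve palsy and improvement of neurological symptoms. A palsy that arose during the wait might first be documented for the study at the discharge exam, within 2 days after the procedure (Protocol 5.7).

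The protocol already asks for a current value of quality of life before the first procedure, and of symptoms before each later one. No reason is given for leaving out the neurological scales before the first.

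**Working it through.** **1. The documents' own figures.** 8.1% + 6.9% = 15.0% per year, as Protocol 7 states. 60 followed + 15 lost = 75 enrolled (Protocol 8.1). Both reproduce. The study has no alpha, power or margin to check.

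**2. How the definition behaves.** Applying Protocol 3.2 to three hypothetical subjects:

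| Baseline mRS | mRS at procedure | After procedure | 6-month mRS | Change from baseline | Change from procedure | Counted as permanent morbidity |
|---|---|---|---|---|---|---|
| 1 | 3 (bleed while waiting) | unrelated neurological AE | 3 | +2 | 0 | yes |
| 1 | 2 (decline while waiting) | stroke, recovers | 2 | +1 | 0 | yes |
| 3 | 1 (recovery while waiting) | procedural stroke | 2 | -1 | +1 | no |

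The first two are counted although mRS is unchanged from the time of treatment. The third is not counted although mRS worsened after treatment. The definition does not require that the stroke or adverse event caused the mRS change. Its exclusion of non-neurological causes does not reach a bleed during the wait.

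**3. Expected events before treatment.** Risk over d days at annual rate r is 1 - (1 - r)^(d/365).

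- r = 0.15, d = 45: 1 - 0.85^(45/365) = 1.98% (linear check 0.15 x 45/365 = 1.85%). In 60 subjects, 60 x 0.0198 = 1.19; in 75, 1.49.
- If only half or a quarter of subjects carry that rate (assumption, since eligibility does not restrict the drainage type): 0.60 or 0.30 of 60.
- d = 90 (assumption, since the exception has no limit): 3.9%, about 2.4 of 60.
- If 5% to 10% of subjects bled recently and waited two weeks (assumption), the cited 35% adds 60 x 0.05 x 0.35 = 1.05 to 60 x 0.10 x 0.35 = 2.1 events.

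These are events before treatment, not misclassified subjects. For illustration, suppose half of the 1.19 left a lasting loss large enough to count, and half of those later had a qualifying event (both assumptions). Then 1.19 x 0.5 x 0.5 = 0.30 subjects would be misclassified as harm. Recovery before treatment, which works the other way, has no rate in the documents and cannot be sized.

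**4. What one subject does.** At the 7.5% permanent morbidity cited in Protocol 7 for transarterial Onyx embolization, 0.075 x 60 = 4.5 are expected. With Clopper-Pearson 95% limits, 4/60 = 6.7% (1.9% to 16.2%) and 5/60 = 8.3% (2.8% to 18.4%).

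**5. With a 7-day window.** 1 - 0.85^(7/365) = 0.31%, or 0.19 of 60, against 1.19 at 45 days.

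**The case against.** The strongest reply is that the plan protects its main conclusions in other ways.

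- **Primary outcomes.** Neither uses baseline mRS. Occlusion is angiographic. Stroke is a new deficit of abrupt onset, counted in the 30 days after the first procedure. This stands. A reader might infer that a stale mRS decides what counts as stroke, but the definition does not use it.
- **Harm hidden by recovery.** A reader might infer that the stroke in the third example is lost to the trial. It is not. If ipsilateral and within 30 days, it counts in the primary safety outcome. If the deficit persists, it falls under the secondary outcome on unresolved device- or procedure-related deficits, which Protocol 3.2 applies even without an mRS change. It escapes only the permanent-morbidity count.
- **Pre-treatment change scored as harm.** A reader might infer that any decline during the wait is charged to PHIL. Under permanent morbidity, a stroke or neurological adverse event is also needed, and adverse events are collected only from hub connection. Such a decline can be counted, but not by itself.
- **Adjudication and relatedness.** Independent physicians adjudicate the primary and secondary outcomes (Protocol 7.4). Onset time is recorded for each adverse event, and disease-related is a defined category (Protocol 7.1, 7.2.1). These will catch some cases, but no neurological score at the time of treatment is required for them to work from.
- **Eligibility.** A reader might infer that a subject whose mRS has risen above 3 may still be treated. Protocol 4 and the definition of enrolled in Protocol 15 require the criteria to be met at enrollment. Only a scheduled re-measurement is missing.
- **Size.** The 15% rate applies to persistent cortical venous drainage, and Protocol 1.2.5 says high-grade lesions should be treated early, so many waits will be short. This also stands. The reference to pre-procedure observations does not fill the gap, because only one pre-treatment mRS is scheduled.

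**Conclusion.** The point holds for secondary and additional outcomes, chiefly permanent morbidity. A site that follows the plan exactly can produce a baseline mRS, NIHSS and symptom exam 45 days old or older, and the permanent-morbidity definition can then misclassify a subject in either direction.

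The figure of about 1.2 of 60 is a ceiling under two assumptions: every subject waits 45 days, and every subject carries the 15% annual rate. Longer justified delays or recent hemorrhage would raise it; shorter waits or lower-risk fistulas would lower it. A reader might take it as the number misclassified. It is not: the working shows 0.30 under illustrative assumptions. It still matters, because the expected count is only about 4.5 and one subject shifts the estimate by 1.7 percentage points. The analysis is descriptive, and Protocol 8.2 and SAP 8.1 foresee comparison with literature rates.

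The documents do not support a claim that either primary outcome is biased or that procedural strokes go unrecorded. This is an inexpensive improvement to how secondary outcomes are measured.

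**What to change.** - **Protocol 5.5.3 and Table 6:** add mRS, NIHSS and the dAVF symptom exam within 7 days before the index procedure, in the window already used for EQ-5D.
- **Protocol 3.2 and 8.2, SAP 4.2 and 8.1:** define baseline, for permanent morbidity and the other neurological change outcomes, as the last assessment before the index procedure.
- **Subjects already treated:** use the last recorded pre-procedure value and report the distribution of the interval from baseline to procedure.

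No new eligibility rule is needed; the repeated mRS would inform the check that the protocol already requires. The cost is two short scales and an exam per subject, a protocol amendment and a sentence in the SAP. Protocol 5.5.3 does not place the EQ-5D at the admission, so sites would have to decide where in the 7 days the assessments fit.
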